4.6.3.2. Laboratory and Adverse Event for Hepatic Safety

Hepatic labs include:

- alanine aminotransferase (ALT),
- aspartate aminotransferase (AST),
- total bilirubin (TBL),
- direct bilirubin (DBL),
- serum alkaline phosphatase (ALP), and
- gamma-glutamyltransferase (GGT).

As specified by the protocol, when criteria are met for hepatic evaluations, investigators will conduct close monitoring of hepatic symptoms and liver tests, perform a comprehensive evaluation for alternative causes of abnormal liver tests, and complete follow-up hepatic safety CRFs.

Analysis	Details		
Abnormal postbaseline categories – hepatic safety parameters	ALT: The number and percentage of participants with a measurement greater than or equal to 1 time $(1\times)$, 3 times $(3\times)$, 5 times $(5\times)$, 10 times $(10\times)$, and 20 times $(20\times)$ the performing laboratory ULN during the postbaseline period will be summarized for all participants with a postbaseline value.		
	AST: The number and percentage of participants with a measurement greater than or equal to 1 time $(1\times)$, 3 times $(3\times)$, 5 times $(5\times)$, 10 times $(10\times)$, and 20 times $(20\times)$ the performing laboratory ULN during the postbaseline period will be summarized for all participants with a postbaseline value.		
	ALP: The number and percentage of participants with a measurement greater than or equal to 2 times (2^{\times}) and 3 times (3^{\times}) the performing laboratory ULN during the postbaseline period will be summarized for all participants with a postbaseline value.		
	TBL: The number and percentage of participants with a measurement greater than or equal to 2 times (2^{\times}) , 5 times (5^{\times}) , and 8 times (8^{\times}) the performing laboratory ULN during the postbaseline period will be summarized for all participants with a postbaseline value.		
	DBL: The number and percentage of participants with a measurement greater than or equal to 2 times (2^{\times}) and 5 times (5^{\times}) the performing laboratory ULN during the postbaseline period will be summarized for all participants with a postbaseline value.		
	GGT: The number and percentage of participants with a measurement greater than or equal to 2 times (2^{\times}) the performing laboratory ULN during the postbaseline period will be summarized for all participants with a postbaseline value.		
Treatment-emergent potentially drug-related hepatic disorders	 Potentially drug-related hepatic disorders are defined using a custom query based on the following SMQs: Broad and narrow terms in the Liver-related investigations, signs and rematering SMQ (20000008) 		
	 Broad and narrow terms in the Cholestasis and jaundice of hepatic origin SMO (20000009) 		
	 Broad and narrow terms in the Hepatitis non-infections SMQ (20000010) Broad and narrow terms in the Hepatic failure, fibrosis and cirrhosis and other liver damage SMQ (20000013) 		
	 Narrow terms in the Liver-related coagulation and bleeding disturbances SMQ (20000015) 		
	These SMQs are a subset of the sub-SMQs comprising the full Hepatic Disorders SMQ. Only the sub-SMQs considered applicable to capturing potentially drug -related hepatic disorders are included.		
	The percentage of study participants with at least one of any of the MedDRA preferred terms from any of the above SMQs will be summarized in addition to the percentages for each MedDRA preferred term.		

The table below lists summary TFLs for the analysis of hepatic laboratory data.

Analysis	Details				
Hepatocellular drug-induced liver injury screening plot (TBL vs ALT or AST)	Each participant's data is plotted based on their maximum postbaseline TBL (y-axis and transaminase (ALT or AST, whichever is higher), regardless of the time betwee the 2 maximum values. Dashed lines represent TBL and transaminase cutoffs of 2× ULN and 3× ULN, respectively. A potential Hy's law case is circled and is defined having a maximum postbaseline TBL equal to or exceeding 2× ULN within 30 days after maximum postbaseline ALT or AST equal to or exceeding 3× ULN, without cholestasis (defined as ALP less than 2× ULN).				
Hepatocellular drug-induced liver injury screening table	The percentages of study participants falling in each of the 3 relevant quadrants of the plot (right upper, left upper, right lower) will be summarized in a table.				
Cholestatic drug-induced liver injury screening plot (TBL vs ALP)	Each participant's data is plotted based on their maximum postbaseline TBL (y-ax and ALP (x-axis), regardless of the time between the 2 maximum values. Lines represent TBL and ALP cutoffs of 2× ULN and 3× ULN, respectively. A potential cholestatic liver injury case is circled and is defined as having a maximum postbaseline TBL equal to or exceeding 2× ULN within 30 days after maximum postbaseline ALP equal to or exceeding 3× ULN.				
Cholestatic drug-induced liver injury screening table	The percentages of study participants falling in each of the 3 relevant quadrants of the plot (right upper, left upper, right lower) will be summarized in a table.				
List of Participants with potential hepatocellular drug-induced liver injury	Includes participants falling in the right upper quadrant in the Hepatocellular Drug- Induced Liver Injury Screening plot Variables to include are unique subject ID, age, sex, race, treatment, max AST, max ALT, max ALP, max TBL				
List of Participants with potential cholestatic drug- induced liver injury	Includes participants falling in the right upper quadrant in the Cholestatic Drug- Induced Liver Injury Screening plot Variables to include are unique subject identifier, age, sex, race, treatment, max AST, max ALT, max ALP, max TBL				

Abbreviations: ALP = alkaline phosphatase; ALT = alanine aminotransferase; AST = aspartate aminotransferase; CRF = case report form; DBL = direct bilirubin; GGT = gamma-glutamyl transferase; MedDRA = Medical Dictionary for Regulatory Activities; SMQ = Standardized MedDRA Query; TBL = total bilirubin; ULN = upper limit of normal.

Planned and unplanned measurements will be included. The measurements do not need to be taken at the same blood draw.

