## 7.1.1. Liver Chemistry Stopping Criteria

The study drug should be interrupted or discontinued if one or more of these conditions occur:

Elevation from baseline	Exception
ALT or AST >8x ULN	
ALT or AST >5x ULN for more than 2 weeks	
ALT or AST >3x ULN and either TBL >2x ULN or	In participants with Gilbert's syndrome, doubling of
INR >1.5	direct bilirubin should be used for drug interruption/
	discontinuation decisions rather than TBL>2x ULN.
ALT or AST $>3x$ ULN with the appearance of fatigue,	
nausea, vomiting, right upper quadrant pain or	
tenderness, fever, rash, and/or eosinophilia (>5%)	
ALP $>3x$ ULN, when the source of increased ALP is	
the liver	
ALP >2.5x ULN and TBL >2x ULN	In participants with Gilbert's syndrome, doubling of
	direct bilirubin should be used for drug interruption/
	discontinuation decisions rather than TBL>2x ULN.
ALP >2.5x ULN with the appearance of fatigue,	
nausea, vomiting, right upper quadrant pain or	
tenderness, fever, rash, and/or eosinophilia (>5%)	
Source: FDA Guidance for Industry: Drug-Induced Live	r Injury: Premarketing Clinical Evaluation, July 2009,
and other consensus guidelines, with minor modification	S

Abbreviations: ALP = alkaline phosphatase; ALT= alanine aminotransaminase; AST = aspartate aminotransferase; FDA = Food and Drug Administration; INR = International normalized ratio; TBL = Total bilirubin level; ULN = Upper Limit of Normal

Resumption of the study drug can be considered only in consultation with the Lilly-designated medical monitor and only if the liver test results return to baseline and if a self-limited non-drug etiology is identified.

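### The Hy's law circle on the SAP's liver screening plot compares the dates of two peaks in one direction, so it can miss participants with concurrent qualifying elevations

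*SAP*

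**What the plan says.** The table in SAP 4.6.3.2 places each participant on the hepatocellular screening plot by maximum postbaseline TBL and maximum postbaseline ALT or AST, with no limit on the time between the two. It then defines the circle: "A potential Hy's law case is circled and is defined" by a "maximum postbaseline TBL equal to or exceeding 2× ULN within 30 days" of the transaminase maximum. The direction is given as "within 30 days after maximum postbaseline ALT or AST equal to or exceeding" 3× ULN. The last condition is absence of cholestasis, which the SAP represents by ALP below 2× ULN.

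The cholestatic plot has a circle of the same form: maximum TBL at or above 2× ULN within 30 days after the maximum "postbaseline ALP equal to or exceeding" 3× ULN.

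Three other statements in the section matter:

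- The quadrant tables give the percentages of participants in the three relevant quadrants, with no timing condition.
- The listings include everyone in the right upper quadrant. Their liver variables are the maximum AST, ALT, ALP and TBL.
- Planned and unplanned measurements both count, and they need not come from the same blood draw.

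**The concern.** The circle is meant to mark transaminase and bilirubin elevations that belong together in time. The rule does not test that. It tests whether one peak date follows another by no more than 30 days. The same table cell uses maximum postbaseline TBL for the value on the y-axis, so the natural reading is the participant's overall maximum.

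Two peaks can be out of order or far apart while the qualifying elevations themselves coincide. The rule can also behave perversely: a participant who would be circled if bilirubin stopped rising inside the window loses the circle if it rises further and peaks after day 30.

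At stake is whether a prespecified liver-safety display marks the participants it says it marks.

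**Working it through.** The plan states no figure to reproduce, so the check applies the definition to time courses.

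**Rules compared.** All require maximum TBL ≥2× ULN and maximum ALT/AST ≥3× ULN. ALP is taken as below 2× ULN throughout.

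- *Literal:* 0 ≤ day(maximum TBL) − day(maximum ALT/AST) ≤ 30. Same-day peaks are assumed to count.
- *Looser:* any TBL ≥2× ULN from 0 to 30 days after the ALT/AST peak.
- *Proposed:* any TBL ≥2× ULN from 0 to 30 days after any ALT/AST ≥3× ULN.

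**Courses.** These are made up to exercise the wording. Values are multiples of ULN, shown as day: value.

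| Course | TBL | ALT | Gap between peaks (days) | Literal | Looser | Proposed |
|---|---|---|---|---|---|---|
| A | 100: 2.5; 110: 4 | 100: 8; 110: 5 | 110 − 100 = 10 | circled | circled | circled |
| B | 95: 4; 100: 2.5 | 95: 6; 100: 8 | 95 − 100 = −5 | no | circled | circled |
| C | 95: 2.5; 100: 1.5 | 95: 6; 100: 8 | 95 − 100 = −5 | no | no | circled |
| D | 100: 1.5; 120: 3; 135: 5 | 100: 8; 120: 5; 135: 3 | 135 − 100 = 35 | no | circled | circled |
| E | 100: 1.0; 120: 1.8; 135: 2.5 | 100: 8; 120: 5; 135: 3.5 | 135 − 100 = 35 | no | no | circled |
| F | Week 12: 3 | Week 12: 5; Week 52: 6 | (12 − 52) × 7 = −280 | no | no | circled |

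The literal rule circles 1 of 6, the looser reading 3 of 6 and the proposed rule 6 of 6. All six courses contain a same-day pair that meets both thresholds: day 100 in A, day 95 in B and C, day 120 in D, day 135 in E and Week 12 in F. All six lie in the right upper quadrant, so the quadrant table and listing include them.

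Course D shows the perverse direction. Had TBL stopped at 3× ULN on day 120, the gap would be 120 − 100 = 20 days and the literal rule would circle it. The further rise to 5× ULN on day 135 removes the circle.

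**How the sampling schedule bears on this.** The Protocol schedules of activities (1.3.1 and 1.3.2) place postbaseline clinical chemistry at Weeks 12, 26, 52, 78 and 83, apart from early termination. The nominal gaps are:

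- Weeks 12 to 26: 14 × 7 = 98 days
- Weeks 26 to 52: 26 × 7 = 182 days
- Weeks 52 to 78: 26 × 7 = 182 days
- Weeks 78 to 83: 5 × 7 = 35 days

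The windows are ±3 days at Week 78 and ±7 days at Week 83, so the last gap runs from 35 − 10 = 25 to 35 + 10 = 45 days. It is the only gap that can fall within 30 days. Elsewhere the circle depends on both peaks being in one draw or on unscheduled repeats. Protocol Appendix 5 (10.5) asks for a repeat within 48 to 72 hours and, if the abnormality persists or worsens, initial monitoring 1 to 3 times weekly. With repeats that close together, the two peak dates can easily differ. One higher ALT after the TBL peak is then enough to remove the circle.

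**The case against.** The strongest reply is that little depends on the circle, and most of that reply stands. It is an annotation on a screening plot. The quadrant table and listing have neither a timing nor an ALP condition. Hepatic follow-up forms under Protocol Appendix 5 are triggered by laboratory thresholds, including TBL alone at 2× ULN when baseline is below 1.5× ULN (known Gilbert's syndrome excepted), and do not depend on the circle. What the reply leaves open is that the listing specifies neither dates nor a flag, so a reader cannot recover from it which right-upper-quadrant participants had concurrent elevations.

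A second reply is that the phrase could mean the highest TBL within the 30-day window. That would restore courses B and D. The SAP does not say so, and C, E and F would still be missed.

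Three stronger readings are tempting, but the documents do not support them:

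- *That a reported number of Hy's law cases will be wrong.* Section 4.6.3.2 plans no such count, table or test.
- *That the circle contradicts Protocol 7.1.1, which lists "ALT or AST >3x ULN and either TBL >2x ULN or" raised INR.* That is a criterion for interrupting or discontinuing study drug. It has no cholestasis condition, and the circle is narrower by design.
- *That participants who enter with ALP between 2× and 2.5× ULN are wrongly barred from the circle.* Excluding ALP at or above 2× ULN is the SAP's own stated cholestasis criterion.

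**Conclusion.** The definition is wrong as written, in a limited way. It leaves uncircled some participants who have a TBL of at least 2× ULN on the same day as, or within 30 days after, an ALT or AST of at least 3× ULN. The cause is that it dates the overall peaks instead of the qualifying values. The cholestatic circle fails in the same way.

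The effect stops at the circles. Tabulated quadrant percentages, membership of the listings, individual hepatic follow-up and all efficacy analyses are unchanged.

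No frequency can be attached. The documents give no expected number of hepatic events and no time courses for them, and the six courses above show mechanisms, not a rate. The conclusion rests on reading maximum postbaseline TBL in the definition as the plotted overall maximum. Under the looser reading the problem shrinks but remains.

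**What to change.** Redefine the hepatocellular flag as any postbaseline TBL ≥2× ULN on the same day as, or within 30 days after, any postbaseline ALT or AST ≥3× ULN. Apply the existing ALP <2× ULN condition to the samples in that window. Give the cholestatic flag matching wording: any TBL ≥2× ULN on the same day as, or within 30 days after, any ALP ≥3× ULN. Leave the plot axes as maxima. Add the flag and the qualifying dates to both listings.

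The new rule still looks forward, so a participant whose TBL reaches 2× ULN only before any ALT/AST reaches 3× ULN stays uncircled. That is then an explicit choice that the listed dates make visible.

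The cost is one sentence per flag, one programming change and two extra items in the listings. A few more points may be circled. The SAP version history says this section was revised to align with the program safety analysis plan, so the wording there should be checked and kept consistent.

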4.6.3.3. Clinical Laboratory Evaluations

For the following selected laboratory measures:

- liver enzyme tests: ALT, ALP, AST, GGT, direct bilirubin and total bilirubin, and
- lipid measures: triglycerides, total cholesterol, LDL-C, and HDL-C (results from fasting samples).

MMRM model (as described in Section 4.6) will be used for the observed values, change from baseline and percentage change from baseline, for which log-transformation will be applied.

Geometric LS means will be provided. Analyses will be provided in both international units (SI) and conventional units (CN) if they are different.

Box plots with descriptive statistics for the observed values and change from baseline will be provided by treatment group and visit.

For other laboratory measures, descriptive summaries will be provided for the observed values and change from baseline by treatment group and visit.

The percentages of patients with elevated or low values meeting specified levels (see Appendix 11, Section 6.11) at any time postbaseline (including scheduled and unscheduled measurements) will be summarized and compared between treatment groups using Fisher's exact test, and risk difference and 95% confidence interval will be reported.

A listing of abnormal laboratory analytes collected quantitatively (high or low during postbaseline using Level 2 definitions) and qualitatively (abnormal during postbaseline) will be provided, including participant identification, treatment group, laboratory sample collection day (that is, days from start of study drug), analyte name, abnormal result, reference low or high limits, and level 2 cut-off value if applicable.

Scatter plots of baseline maximum baseline-by-maximum postbaseline measurements and minimum baseline-by-minimum postbaseline measurements will not be created a-priori. They may be created if warranted after review of the planned tables and figures, using Figures 6.3 and 6.4 from the Analysis and Displays for Labs white paper (PHUSE 2022) as the model. ADaM datasets will include variables to enable the creation of scatter plots for use in either an interactive tool or for ad-hoc figures.

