For continuous safety variables (for example, laboratory measures, vital signs, and weight), MMRM or ANCOVA models will be used. For categorical safety variables (for example, AEs, incidence of hypoglycemia, treatment-emergent abnormal laboratory measurements), either Fisher's exact test or logistic regression will be used for treatment comparison.

Further details for assessing all safety measures will be described in the SAP.

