4.6.3.4. Vital Signs and Physical Characteristics

The planned summaries are provided in the table below. The measurements analyzed for vital signs and physical characteristics include systolic BP, diastolic BP, pulse, weight, and BMI:

Analysis Type	Analysis Details						
Observed	• Includes all participants in the Safety Analysis Set who have both a baseline and at least 1						
values and	postbaseline observation.						
change by visit	• MMRM model (as described in Section 4.6) will be used.						
	See also: Table 6.2 from the Analyses and Displays for Labs white paper (PHUSE 2022)						
Summary by	• Definitions provided in Tables 31-33 from FDA's September 2022 Standard Safety Tables						
category	and Figures document will be used for the numerator.						
	○ Systolic BP (mm Hg): Level 1 (low): <90, Level 1 (high): ≥90, Level 2 (high):						
	≥120, Level 3 (high): ≥140, Level 4 (high): ≥160, Level 5 (high): ≥180						
	• Diastolic BP (mm Hg): Level 1 (low): <60, Level 1 (high): >60, Level 2 (high):						
	>90, Level 3 (high): >110, Level 4 (high): ≥120						
	• Includes participants with at least one postbaseline measurement.						
	• Statistical comparisons (using methods described in Section 4.6) will be included.						
Participants	For weight, cutoffs informed by CTCAE version 5 (Grades 1-3) will be used:						
meeting CTC	○ (Loss) decrease: Level 1: \geq 5%, Level 2: \geq 10%, Level 3: \geq 20%						
grade changes	 (Gain) increase: Level 1: ≥5%, Level 2: ≥10%, Level 3: ≥20% 						
in weight	Includes participants with both a baseline and at least 1 postbaseline observation.						
	• Statistical comparisons (using methods described in Section 4.6) will be included.						

Scatter plots (to support vital sign evaluations): Scatter plots of maximum-by-maximum measurements and minimum-by-minimum measurements will not be created a-priori. They may be created if warranted after review of the planned tables and figures, using Figures 6.3 and 6.4 from the Analysis and Displays for Labs white paper (PHUSE 2022) as the model. ADaM datasets will include variables to enable the creation of scatter plots for use in either an interactive tool or for ad-hoc figures.

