4.9. Changes to Protocol-Planned Analyses

There are no changes to the analyses described in the protocol but additional details are provided.

5. Sample Size Determination

Approximately 939 participants will be randomly assigned to LY3209590 and insulin degludec in a 2:1 ratio. With the assumption of 15% dropout at Week 26 (Visit 22), approximately 532 and 266 participants will complete 26 weeks of treatment on LY3209590 and insulin degludec, respectively.

The primary objective of this study is to test the hypothesis that LY3209590 is noninferior to insulin degludec on glycemic control as measured by change from baseline to Week 26 (Visit 22) in HbA1c in participants with T2D currently on basal insulin.

Assuming a NIM of 0.4%, no true difference between treatment groups, and a SD of 1.1%, 798 completers (532 on LY3209590 and 266 on insulin degludec) will provide greater than 99% statistical power to show noninferiority between LY3209590 and insulin degludec using the upper limit of a 2-sided 95% confidence interval (LY3209590 – insulin degludec). This sample size also has at least 95% statistical power to show noninferiority between LY3209590 and insulin degludec) and insulin degludec using a 0.3% NIM at Week 26 (Visit 22).

The 798 completers will provide 95% statistical power to demonstrate the superiority (LY3209590 vs. insulin degludec) of change in HbA1c from baseline to 26 weeks (assuming a SD of 1.1% and true mean difference is -0.3%) using the alpha of 0.05.

The 798 completers will provide at least 95% statistical power to show the superiority of the percentage of time in glucose range between 70 and 180 mg/dL (3.9 and 10.0 mmol/L) inclusive during the CGM session prior to Week 26 (Visit 22) between LY3209590 and insulin degludec (assuming a SD of 18% and true mean difference is 5%) at alpha = 0.05.

The 798 participants will provide at least 80% statistical power to show the superiority of the event rate of clinically significant nocturnal hypoglycemia (<54 mg/dL [3.0 mmol/L] or severe) during treatment phase up to Week 78 (assuming event rate of 0.67 [SD = 2.6] and 1.1 [SD = 2.6] events per participant per year for LY3209590 and insulin degludec, respectively) using a negative binomial distribution at alpha = 0.05.

6. Supporting Documentation

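### SAP 4.6.3.3 tests laboratory abnormalities at any time postbaseline without a baseline condition, although Protocol 9.3.5 names treatment-emergent ones; this weakens the test for fixed cut-offs that are often met at baseline

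*SAP*

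**What the plan says.** Protocol 9.3.5 sets the comparison in general terms: "For categorical safety variables (for example, AEs, incidence of hypoglycemia, treatment-emergent abnormal laboratory measurements), either Fisher's exact test or logistic regression" is to be used. Treatment-emergent appears there as an example and is not defined; further detail is left to the SAP.

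SAP 4.6.3.3 takes the percentage of patients with elevated or low values meeting specified levels, which "at any time postbaseline (including scheduled and unscheduled measurements) will be summarized and compared between treatment groups using Fisher's exact test", with a risk difference and 95% confidence interval. It sets no condition on baseline. It sends the reader to Appendix 11 for the levels, but Appendix 11 is the Japan analysis; the levels are in Appendix 12. The hepatic categories in SAP 4.6.3.2 have the same form: counts beyond multiples of "the performing laboratory ULN during the postbaseline period will be summarized for all participants with a postbaseline value".

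The table in SAP 4.1 defines a baseline period for elevated or low categories. It runs from screening to the first day of study treatment and includes scheduled and unscheduled values. The fixed-threshold laboratory tests do not use it. On departures from the protocol, SAP 4.9 states: "There are no changes to the analyses described in the protocol but additional details are provided".

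**The concern.** A participant already beyond a fixed cut-off before the first dose will usually be beyond it again at some postbaseline visit, whichever insulin was assigned. Counting that participant as an event adds the same non-informative events to both arms and hides part of any difference in new abnormalities.

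Many Appendix 12 Level 1 cut-offs are mild: triglycerides >150, total cholesterol >200, LDL >130, HDL <40 in males and <50 in females, BUN >23 and uric acid >7.0 (all mg/dL). The eligibility criteria admit pre-existing abnormality, for example an eGFR as low as 20 mL/min/1.73 m².

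Liver and lipid measures also have a baseline-adjusted MMRM. Other analytes have only descriptive summaries besides this Fisher test, so for them it is the one planned between-arm test of the laboratory values themselves. Baseline-by-postbaseline scatter plots are not planned a priori.

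**Working it through.** The documents state no power or event rate for these tests, so there is no figure of the plan to reproduce. The check has two parts.

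**Which rows are affected.** In Appendix 12, creatinine (multiples of baseline), eGFR (percentage decrease from baseline) and the hemoglobin-change rows are already relative to baseline and are unaffected. The remaining chemistry, lipid and blood-count rows are fixed thresholds.

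**Size of the dilution.** Inputs from the documents: 626 and 313 participants (Protocol 1.1). Two-sided 0.05 is taken over from the protocol's wording for model-based tests. Assumed inputs, because the documents give none:
- q: share abnormal at baseline, equal in both arms by randomization
- r: share of those who are abnormal again postbaseline, equal in both arms
- p1 and p0: new onset on LY3209590 and degludec among those not abnormal at baseline

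The event rate as written is q·r + (1 − q)·p in each arm, so the risk difference is (1 − q)(p1 − p0). The treatment-emergent version compares p1 with p0 on (1 − q) of each arm.

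Worked case with q = 40%, r = 97%, p1 = 30%, p0 = 20%:
- As written: 0.4×0.97 + 0.6×0.30 = 0.568 against 0.4×0.97 + 0.6×0.20 = 0.508. The difference is 0.060, with standard error √(0.568×0.432/626 + 0.508×0.492/313) = 0.0345, a ratio of 1.74.
- Treatment-emergent: 0.30 against 0.20 on 376 and 188 participants. The difference is 0.100, with standard error √(0.30×0.70/376 + 0.20×0.80/188) = 0.0375, a ratio of 2.66.

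The restricted comparison does better despite its smaller denominator. Exact enumeration of two-sided Fisher power gives:

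| q | r | New onset, LY3209590 vs degludec | Power as written | Power, not abnormal at baseline |
|---|---|---|---|---|
| 40% | 97% | 30% vs 20% | 39.3% | 72.1% |
| 20% | 97% | 30% vs 20% | 65.4% | 83.5% |
| 60% | 97% | 30% vs 20% | 22.7% | 53.1% |
| 2% | 97% | 30% vs 20% | 89.0% | 90.3% |
| 2% | 97% | 10% vs 5% | 65.6% | 75.3% |
| 10% | 100% | 10% vs 5% | 38.9% | 71.0% |
| 30% | 100% | 10% vs 5% | 17.5% | 58.8% |
| 30% | 50% | 10% vs 5% | 22.5% | 58.8% |

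Simulation of the first row gave 38% and 71%, in agreement. The last row shows that the loss does not depend on near-complete persistence. The fourth shows that it almost disappears when baseline abnormality is rare and onset is common.

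**The case against.** The strongest objection is that the SAP does not breach a definition. The protocol uses treatment-emergent once, as an undefined example, and leaves the details to the SAP. The SAP version history says these safety sections were revised, and Appendix 12 added, to align with the program safety analysis plan. That plan is not available here, so the any-postbaseline convention may be deliberate. This stands: a reader might infer departure from a protocol definition, but the documents show only an undefined term that was not carried over, with no change declared.

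A reader might also infer that a laboratory safety signal would go undetected. The documents do not support that:
- Triglycerides, total cholesterol, LDL and HDL have an MMRM.
- Protocol 8.2.4 requires clinically relevant laboratory changes to be reported as adverse events, and the TEAE analysis takes baseline severity into account.
- Hypokalemia and hepatic disorders have their own treatment-emergent searches.
- Change from baseline is summarized by arm and visit, and a listing at Level 2 is planned.
- Most analytes have Level 2 and Level 3 rows (for example BUN >31, triglycerides >500), where fewer should be abnormal at baseline.

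This cover is real but partial. For the remaining analytes none of it is a between-arm test of the laboratory values.

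A third tempting reading extends the point to blood pressure, where SAP 4.6.3.4 tests rows such as "Level 1 (low): <90, Level 1 (high): ≥90" for systolic pressure. Nearly everyone will meet systolic ≥90 or diastolic >60 at some visit, so those rows are uninformative. They hide nothing, however: the other levels and an MMRM cover blood pressure, and the protocol's treatment-emergent wording concerns laboratory measurements only.

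**Conclusion.** The point holds for the fixed-threshold laboratory rows in SAP 4.6.3.3, chiefly Level 1 rows with common baseline abnormality. The protocol names treatment-emergent abnormalities, the SAP tests any postbaseline abnormality, and neither SAP 4.6.3.3 nor 4.9 explains the difference.

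With equal baseline prevalence and persistence in the two arms, the direction is certain: the risk difference shrinks by the factor (1 − q). The size rests on assumed prevalence, persistence and onset. Across the cases shown, the loss of power runs from about 1 percentage point (89.0% against 90.3%) to about 41 (17.5% against 58.8%). These tests carry no multiplicity adjustment and no power target, so the consequence is a blunter safety screen; no confirmatory conclusion is affected.

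**What to change.** In SAP 4.6.3.3, for the fixed-threshold rows, make the tested comparison treatment-emergent:
- Numerator: participants in the denominator who meet the level postbaseline.
- Denominator: participants with a postbaseline value who did not meet that level in the baseline period defined in SAP 4.1.

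Keep the any-postbaseline percentages and risk difference for all participants alongside it. This preserves alignment with the program safety analysis plan and keeps participants abnormal at baseline visible. Leave the baseline-relative rows as they are. Correct the pointer from Appendix 11 to Appendix 12.

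The cost is SAP wording and one extra denominator in the table programs; no new data are needed. The downside is a smaller denominator for each analyte. Participants already beyond a level at baseline, even on one transient screening value, are then tested only at higher levels, and uric acid has none. The all-participant column is the safeguard for them.
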